### 12.6.3. Safety

Extent of Exposure	

 
Number of days of exposure to study drug will be calculated based on the formula: Duration of Exposure in Days = Treatment Stop Date – (Treatment Start Date) + 1 The number of days exposure therefore does not take into account dose interruptions.
 
Participants who were randomized but did not report a treatment start date will be categorised as having zero days of exposure.
 
Actual amount taken (number of tablets) = Total tablets dispensed – Total tablets returned – Total tablets lost.
 
Females will take 1 mg everyday (2*0.5mg tables) and males will take 2 mg (2*1mg). So, the actual dose (mg) taken will be the same as actual amount taken for males and for females it will be actual amount taken divided by 2.
 
The cumulative actual dose (mg) will be the sum of the actual doses taken.
 
	
Adverse Events	
Onset Time Since 1st Dose (Days)	If Treatment Start Datetime $\leq$ AE Onset Datetime , then AE Onset Datetime - Treatment Start Datetime +1 If time part is missing in any of the Datetime, then use the Treatment Start date and AE

Extent of Exposure	
	Onset date in calculation and missing otherwise.
Duration (Days)	AE Resolution Datetime – AE Onset Datetime + 1 If time part is missing in any of the Datetime, then use the AE Resolution date and AE Onset date in calculation and missing otherwise.
Drug-related	If the question 'is there a reasonable possibility that AE may have been caused by the Study Treatment' is marked 'YES' on CRF or is missing.

MRI

 
Body Surface Area (BSA) (m^2) = 0.007184 * Weight (kg)0.425 * Height (cm)0.725
 
Left Ventricular End Systolic Volume Index (LVESVi) = <math>\frac{LVESV}{\text{Body Surface Area}}</math>
 
Left Ventricular End Diastolic Volume Index (LVEDVi) = <math>\frac{LVEDV}{\text{Body Surface Area}}</math>
 

Adverse Events
Adverse Events of Special Interest (AESI))
The following table presents the AESI. AESI which are not SMQs are made up of a selection of preferred terms (PTs) defined by GSK. The complete list of AESI, including the PTs which contribute to each of the AESI will be provided by Safety and Medical Governance using the MedDRA version current at the time of reporting.

AESI	Group of terms (MedDRA SMQ, HLT or individual PTs)																		
Drug related hepatic disorders	Drug related hepatic disorders – comprehensive search (SMQ)																		
Reproductive organ effects, male	Prostatic neoplasms and hypertrophy HLT plus selected preferred terms: Prostatic specific antigen abnormal Prostatic specific antigen increased																		
Reproductive organ effects, female	Female gonadal function disorders HLT (includes PT of Hirsutism and Virilism)																		
Virilism in females	Hirsutism PT, Virilism PT, Acnes HLT, Dysphonia PT																		
Dyslipidaemia	Dyslipidaemia SMQ																		
Bone effects	Osteoporosis/osteopenia (SMQ), Plus, selected Fracture PTs (57 terms)																		
	
  
 MedDRA PT	PT Code	
   
 Ankle fracture	10002544	
 
 Bone decalcification	10070817	
 
 Bone disorder	10005956	
 
 Bone fragmentation	10064211	
 
 Clavicle fracture	10009245	
 
 Comminuted fracture	10052614	
 
 Complicated fracture	10010149	
 
 Compression fracture	10010214	
  
	MedDRA PT	PT Code	Ankle fracture	10002544	Bone decalcification	10070817	Bone disorder	10005956	Bone fragmentation	10064211	Clavicle fracture	10009245	Comminuted fracture	10052614	Complicated fracture	10010149	Compression fracture	10010214
	MedDRA PT	PT Code																	
	Ankle fracture	10002544																	
	Bone decalcification	10070817																	
	Bone disorder	10005956																	
	Bone fragmentation	10064211																	
	Clavicle fracture	10009245																	
	Comminuted fracture	10052614																	
	Complicated fracture	10010149																	
Compression fracture	10010214																		

Epiphyseal fracture	10053962
Facial bones fracture	10016042
Fibula fracture	10016667
Foot fracture	10016970
Fracture delayed union	10017081
Fracture displacement	10053206
Fracture reduction	10057609
Fractured coccyx	10049164
Fractured skull depressed	10017310
Greenstick fracture	10018720
Hand fracture	10019114
Humerus fracture	10020462
Impacted fracture	10066386
Internal fixation of spine	10069749
Jaw fracture	10023149
Lower limb fracture	10061599
Open fracture	10030527
Osteocalcin decreased	10050940
Osteonecrosis	10031264
Osteonecrosis of jaw	10064658
Patella fracture	10034122
Scapula fracture	10039579
Skeletal injury	10061363
Skull fracture	10061365
Skull fractured base	10040960
Sternal fracture	10042015
Stress fracture	10042212
Tibia fracture	10043827
Torus fracture	10066094
Traumatic fracture	10049514
Ulna fracture	10045375
Upper limb fracture	10061394
Vertebral wedging	10065317
Atypical fracture	10072395
Avulsion fracture	10066184
Chance fracture	10073162
Limb fracture	10074551
Osteochondral fracture	10073853
Periprosthetic fracture	10069135
Spinal fusion fracture	10074807
Fracture malunion	10017085
Fracture nonunion	10017088
Craniofacial fracture	10077603
Spinal flattening	10077756
Bone metabolism biochemical marker increased	10078949
Subchondral insufficiency fracture	10079864

	Maisonneuve fracture	10081343
	Degenerative bone disease	10081730
	Internal fixation of fracture	10022576
Cardiovascular effects	See the table below.	
Hypersensitivity	Hypersensitivity (SMQ) narrow, Angioedema (SMQ) narrow, Anaphylactic reaction (SMQ) narrow	
Hostility/aggression	Hostility/aggression (SMQ)	
Sexual desire disorders	Sexual desire disorders HLT	
Embolic and thrombotic events	Embolic and thrombotic events (SMQ)	

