3.3.1. Risk Assessment

Potential Risk of Clinical Significance	Summary of Data/Rationale for Risk	Mitigation Strategy
Investigational Product (IP) GSK2881078		

Elevation of Alanine Aminotransferase (ALT) and other liver function tests (AST, bilirubin, total and direct).
	
This has been observed in a variety of SARMs and was observed (minimal) in the 14-day and 13-week rat toxicity studies with administered GSK2881078.
 
One subject had elevations of Liver Function Tests (LFTs) in Phase 1a, but it was unclear if this was related to drug. Transient elevations in ALT without concomitant changes in bilirubin were observed in Phase 1b.
	
Monitoring of liver function tests will be in place at all clinic visits. This study will use follow up procedure that were used in Phase I of development of GSK2881078 for participants who have met liver stopping criteria, as detailed in Section 8.1.1 of this protocol.

Effects on reproductive organs/tissues:
 
Men – testes, epididymis, and prostate gland
 
Women – ovaries and uterus
	
These are recognized effects of SARM pharmacology and show recovery on discontinuation of dosing.
 
Test article-related organ weight and/or microscopic changes were observed in the gonads and other associated reproductive tissues in rat 14-day and 13-week toxicity studies administered GSK2881078. All test article-related microscopic findings were reversible after a 4- or 8- week off dose period. Test article-related effects were observed in male mating, fertility, gonadal function, and male-mediated development in a male rat fertility study.
 
In phase I studies, all male subjects dosed with
	
Males with PSA levels >4.0 ng/mL will be excluded.
 
Females will be post-menopausal.
 
Participants will be monitored at baseline, Day 28, Day 56, Day 89 and follow-up for changes in the following levels:
 
 • luteinizing hormone • follicle stimulating hormone • testosterone • free testosterone (calculated) • estradiol

Potential Risk of Clinical Significance	Summary of Data/Rationale for Risk	Mitigation Strategy

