	GSK2881078 displayed reversible reductions in testosterone. No changes in PSA were recorded. Reversible reductions in sex hormone binding globulin were observed in both men and women. There were no clinically significant changes in FSH, LH, estradiol or progesterone.	
 • dihydrotestosterone • sex hormone binding globulin
Lowering of High-Density Lipoprotein (HDL) levels - A class effect of SARMs	All subjects dosed with GSK2881078 exhibited a reduction in HDL Cholesterol in Phase I studies. This reduction exhibited a dose response, with evidence of maximal pharmacology at a reduction of approximately 30-40% from baseline. This reduction was accompanied by a similar reduction proportionally in ApoA1. In all cases HDL Cholesterol returned to baseline on discontinuation of dosing.	Monitoring lipid profiles to confirm decreases seen on treatment, and whether lipid parameters return to baseline following discontinuation of study treatment. Lipid panels will be monitored at baseline, Day 56, Day 89 and at follow-up.
Bone effects	Minimal trabecular atrophy was observed in female rats at all doses in a 13- week toxicity study. This finding was not observed in male rats or dogs of either sex after 13 weeks of GSK2881078 administration.	
Bone turnover markers will be measured at baseline, Day 56, Day 89 and at follow-up. Bone biomarkers will include:
 
 • procollagen type I N propeptide (s-PINP) for formation • C-terminal telopeptide of type I collagen (s-CTX)
Anabolic abuse	Since this compound builds lean body mass, there is potential risk for anabolic abuse through illicit use of the drug by body builders.	Use of compound will be restricted to participants enrolled in study. Sites will have in place secure storage for compound supply. Sites to confirm restricted use of compound by enrolled participants at each study visit. Sites will be inspected for secure storage.

Potential Risk of Clinical Significance	Summary of Data/Rationale for Risk	Mitigation Strategy

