### 8.2. Adverse Events of Special Interest Analyses

The table in [Section 12.6.3](#) (“Safety”) presents the Adverse Events of Special Interest (AESI) and the groups of terms that they comprise. AESI which are not standardized MedDRA queries (SMQs) comprise a selection of PTs defined by GSK. The final list of AESIs, and the PTs that contribute to each of the AESIs, will be provided by Safety and Medical Governance (SMG), using the MedDRA version current at the time of reporting. This list will be finalized prior to unblinding the database.

Changes to the MedDRA dictionary may occur between the start of the study and the time of reporting. Furthermore, emerging data from on-going studies may highlight additional AESI. Therefore, the list of AESI, and the terms included for each AESI, will be based on the safety review team (SRT) agreements in place at the time of reporting. The details of the planned displays are provided in [Appendix 11](#): List of Data Displays.

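### As printed, the male reproductive AESI group covers only the prostate, one of the three male organs that the protocol names as at risk

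*SAP*

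**What the plan says.** Protocol 3.3.1 lists effects on reproductive organs as a risk of clinical significance and, for men, names "testes, epididymis, and prostate gland". Its supporting data are largely gonadal. In the rat toxicity studies, organ-weight and/or "microscopic changes were observed in the gonads and other associated reproductive tissues". Effects were also seen on "male mating, fertility, gonadal function, and male-mediated development in a male rat fertility study". In phase I, all dosed men "displayed reversible reductions in testosterone. No changes in PSA were recorded". Protocol 5.5 names suppression of testosterone, beside raised liver tests and lowered HDL, among the adverse events of potential clinical significance.

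SAP 12.6.3 prints the AESI groups and their terms. The group labelled 'Reproductive organ effects, male' consists of "Prostatic neoplasms and hypertrophy HLT plus selected preferred terms: Prostatic specific antigen abnormal Prostatic specific antigen increased".

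The printed list is not final. SAP 12.6.3 says "The complete list of AESI, including the PTs which contribute to each of the AESI will be provided by Safety and Medical Governance", and SAP 8.2 adds of the same list, "This list will be finalized prior to unblinding the database".

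The AESI groups feed Table 3.14 in SAP 12.11.7, which is marked for the headline results.

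**The concern.** The label promises male reproductive organs in general, while the printed terms search one of them. Safety is a primary objective, and an AESI table exists to gather events for risks named in advance. If the terms were used as printed, the male row could show zero while a testicular event sat elsewhere in the report, and a reader could take that zero as reassurance about organs the row never searched.

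The laboratory-type terms show the same narrowness. The row holds two PSA terms and none for testosterone. In phase I, testosterone fell in every dosed man and PSA did not move.

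**Working it through.** No figure in the plan bears on this point, so the check is a comparison of lists.

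**Step 1: organs against printed terms.** The inputs are the three male organs in Protocol 3.3.1 and the three entries for men in SAP 12.6.3: one high-level term (HLT) on prostatic neoplasms and hypertrophy, and two preferred terms for abnormal and increased PSA.

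| Male organ (Protocol 3.3.1) | Entries reaching it, by name |
|---|---|
| Testes | 0 of 3 |
| Epididymis | 0 of 3 |
| Prostate | 3 of 3 |

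The group therefore reaches 1 of 3 organs. None of its entries is a testosterone term.

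**Step 2: do other groups fill the gap?** The other groups printed in SAP 12.6.3 are hepatic disorders, female reproductive effects, virilism in females, dyslipidaemia, bone, cardiovascular, hypersensitivity, hostility/aggression, sexual desire disorders, and embolic and thrombotic events. None names a testicular, epididymal or low-testosterone term. The sexual desire group touches reproductive function but by its name is not an organ group.

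**Step 3: the effects in Protocol 5.5 against the AESI groups.**

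| Effect named in Protocol 5.5 | Printed AESI group |
|---|---|
| Raised liver tests | Drug related hepatic disorders |
| Lowered HDL | Dyslipidaemia |
| Testosterone suppression | None by name |

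**Step 4: could these events be reported as adverse events?** Yes. Protocol 9.5.4 has clinically relevant laboratory changes recorded in the AE section of the case report form. Protocol Appendix 5 counts a laboratory abnormality as an AE when the investigator judges it clinically significant. A testosterone decrease can reach the AE data by that route, and a testicular or epididymal disorder can be reported directly.

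**Step 5: where would such an event appear?**

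| Display | Counted or shown? |
|---|---|
| Table 3.14, male reproductive row (headline) | No, if the printed terms are used |
| Table 3.1, all AEs by SOC and PT (headline) | Yes |
| Listing 14, all AEs | Yes |
| Tables 3.25 and 3.35, Figure 3.3, Listing 47 | Testosterone values, whether or not an AE is reported |

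The gap is confined to one grouped row.

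**The case against.** The strongest reply is that the list is provisional and that the SAP already assigns its completion to the right group at the right time. This stands and limits the point: the omission matters only if the printed terms are carried forward. It does not dispose of the point. Neither SAP 8.2 nor 12.6.3 asks for the final list to be checked against Protocol 3.3.1. Nor is the printed table a bare placeholder: the bone group already carries 57 selected terms, including a laboratory term for decreased osteocalcin.

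Second, neither document requires an AESI group to mirror every organ in the risk table. The monitoring that Protocol 3.3.1 sets out for the reproductive risk is hormonal, and the SAP tabulates those hormones. That is correct, so no rule is broken. What remains is a group whose definition is narrower than its label.

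Third, AE terms may detect little here. The animal findings were organ-weight and microscopic changes or fertility effects, the schedule has no semen analysis or testicular imaging, and the minimum physical examination in Protocol 9.5.1 lists no genital examination. Few events may be coded, which is a reason to claim no effect size. It also means that reported AEs are, apart from hormone values, the main route by which such a problem would show.

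Fourth, the PSA terms are defensible, because prostate effects limit the use of testosterone (Protocol 3 and 3.2). They should stay.

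Two stronger readings are tempting, and the documents do not support them. A reader might infer that testicular events would go unreported; Table 3.1 and Listing 14 show otherwise. A reader might also infer a matching gap for women. That group is defined by "Female gonadal function disorders HLT (includes PT of Hirsutism and Virilism"), and the contents of that HLT are not given, so nothing can be concluded about it.

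**Conclusion.** The point holds as a minor one. By name, all 3 entries in the male group are prostatic and reach 1 of the 3 organs that the protocol names. If kept, they would leave testicular and epididymal AEs, and testosterone decreases reported as AEs, out of that row of Table 3.14. No effect size is claimed, since the documents give no expected rate for these events. No test or decision changes either, because SAP 2.4 plans no formal safety comparisons.

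Three assumptions carry the conclusion:

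- The printed terms survive into the final list.
- The prostate HLT contains what its name says; its MedDRA contents are not in the documents.
- Table 3.14 shows each AESI group as its own row. Its programming note describes only cardiovascular and liver pages, so the reproductive layout is not shown.

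**What to change.** When Safety and Medical Governance finalises the AESI list before unblinding:

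- Add testicular and epididymal disorder terms to 'Reproductive organ effects, male'.
- Add hypogonadism and decreased-blood-testosterone terms, because Protocol 5.5 names testosterone suppression among the AEs of potential clinical significance.
- If the terms are not added, rename the row 'Prostate effects' so that the label matches what is searched.

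The work is a longer term list, drawn up by the group that already owns it and applied to AEs already collected and coded. The only downside is possibly a few more events in the AESI table. No data collection or analysis method changes.

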**Cardiovascular effects AESI**

AESI	AESI Subgroup	Sub-SMQ	Scope
Cardiovascular effects	Cardiac arrhythmia	Arrhythmia related investigations, signs and symptoms (SMQ)	Broad
		Bradyarrhythmia terms, nonspecific (SMQ)	Broad
		Conduction defects (SMQ)	Broad
		Disorders of sinus node function (SMQ)	Broad
		Cardiac arrhythmia terms, nonspecific (SMQ)	Broad
		Supraventricular tachyarrhythmias (SMQ)	Broad
		Tachyarrhythmia terms, nonspecific (SMQ)	Broad
		Ventricular tachyarrhythmias (SMQ)	Broad
	Cardiac failure (SMQ)		Broad
	Ischaemic heart disease (SMQ)		Broad
	Hypertension (SMQ)		Broad
	Central nervous system haemorrhages and cerebrovascular conditions (SMQ)		Broad
	Cardiomyopathy (SMQ)		Narrow

**ECG Parameters**

**General**

- The summary should be based on average value of triplicate ECG readings obtained over a brief recording period (missing readings will not be counted).

**Eligibility Criteria**

- The QT values at screening will be using for the eligibility checking of subjects.

ECG Parameters
Stopping Criteria

A subject who meet either of the bulleted criteria below will be withdrawn from the study:
 
 
• QT interval corrected for heart rate by Bazett's formula (QTcB) or QT interval corrected for heart rate by Fridericia's formula (QTcF) >450 msec
 
• QT interval corrected for heart rate (QTc) >480 msec in participants with Bundle Branch Block based on a single ECG.
 

Laboratory Parameters
General

 
• All clinical laboratory tests will be based on central laboratory assessments only. If a laboratory value which is expected to have a numeric value for summary purposes, has a non-detectable level reported in the database, where the numeric value is missing, but typically a character value starting with '<x' or '>x' (or indicated as less than x or greater than x in the comment field) is present, the number of significant digits in the observed values will be used to determine how much to add or subtract in order to impute the corresponding numeric value.             
 
○ Example 1: 2 Significant Digits = '< x' becomes x - 0.01
 
○ Example 2: 1 Significant Digits = '> x' becomes x + 0.1
 
○ Example 3: 0 Significant Digits = '< x' becomes x - 1
 
 
 

Laboratory Toxicity Grade															

 
• Toxicities will be based on FDA guidance 'Common Terminology Criteria for adverse events v4.03 (CTCAE) defined by NCI-CTEP (National Cancer Institute – Cancer Therapy Evaluation Program).
 
• When summarising toxicity grades for such parameters, they will be categorised as to whether they are above or below the normal range.
 
 
  
 Parameter	Below Normal Range	Above Normal Range	
   
 Fasted glucose	Hypoglycaemia	Hyperglycaemia	
 
 Sodium	Hyponatremia	Hypernatremia	
 
 Potassium	Hypokalemia	Hyperkalemia	
 
 Calcium	Hypocalcemia	Hypercalcemia	
  
	Parameter	Below Normal Range	Above Normal Range	Fasted glucose	Hypoglycaemia	Hyperglycaemia	Sodium	Hyponatremia	Hypernatremia	Potassium	Hypokalemia	Hyperkalemia	Calcium	Hypocalcemia	Hypercalcemia
Parameter	Below Normal Range	Above Normal Range													
Fasted glucose	Hypoglycaemia	Hyperglycaemia													
Sodium	Hyponatremia	Hypernatremia													
Potassium	Hypokalemia	Hyperkalemia													
Calcium	Hypocalcemia	Hypercalcemia													

Hepatitis Status

 
• Hepatitis B and C will be determined using antibody (IgM or IgG) at the screening or within 3 months prior to first dose of study treatment. If there is evidence of Hepatitis C antibodies at the screening visit, then Hepatitis C viral RNA PCR is required to exclude active infection. This sample is not needed if Hepatitis C screening is negative
 
• Antibody (IgM or IgG) status with 'BORDERLINE' or 'REACTIVE' will be considered Positive
 
• A subject will be considered positive for hepatitis B virus (HBV) if they have a positive surface antigen (HBsAg) during screening. Subjects positive for HBV are not allowed to enter the study
 

COPD Exacerbation Event Count

 
• The total number of exacerbation events is determined by summing the number of times there is a non-missing "Date of Onset" on the exacerbation CRF page" for a subject
 
• The number of exacerbating patients refers to the count of the unique patient in the COPD Exacerbation CRF data. In other words, it is the total number of patients who experience one or more exacerbations defied in the first bullet.
 

